2. RATIONALE, OBJECTIVES, AND BENEFIT - RISK ASSESSMENT

2.1 RATIONALE FOR PERFORMING THE TRIAL

Until recently, IPF was essentially an untreatable disease. With the availability of specific antifibrotic drugs like nintedanib and pirfenidone, a major advance in the management of IPF has been achieved. Although both drugs are approved for the treatment of all IPF patients (with the exception of pirfenidone in Europe and other countries where it is approved only for “mild to moderate IPF”), patients with advanced lung function impairment have been typically excluded from the most recent clinical trials in IPF.

In contrast to patients with more preserved lung function, abnormalities of the pulmonary vasculature due to continuous destruction of the vasculature by fibrosis and aberrant vascular remodeling, leading to decreased levels of resting and exercise-induced production of nitric oxide, are more common in patients with advanced lung function impairment, specifically in patients with advanced impairment in diffusion capacity. Since nitric oxide is a potent pulmonary vasodilator, reduced levels are associated with pulmonary vasoconstriction and impaired gas exchange.

Nintedanib is an inhibitor of tyrosine kinases (including the PDGF, VEGF and FGF receptors). By inhibiting these receptors, nintedanib regulates cellular proliferation, survival, migration and differentiation, processes which are involved in the profibrotic process of IPF [[P08-08684](#); [P14-02860](#)]. The phase II and III clinical studies showed that nintedanib slowed IPF disease progression by reducing the annual lung function decline and potentially the risk for acute exacerbations, however no clinically relevant beneficial effect on health related quality of life or other patient-related outcomes measures was observed [[P14-07514](#); [P11-11216](#)].

Sildenafil, a PDE5 inhibitor approved for the treatment of PAH, stabilizes the second messenger of nitric oxide (cGMP) which leads to pulmonary vasodilation. Although the STEP-IPF trial failed to meet its primary outcome of change in 6-minute walk distance of $\geq 20\%$ at week 12, it showed promising results in secondary endpoints with clinically significant differences in the degree of dyspnea and quality of life, as well as in gas exchange parameters [[R12-3686](#)].

Combining these two drugs with different molecular targets might ultimately provide additional benefits to patients with IPF and advanced lung function and gas exchange impairment: nintedanib by slowing the disease progression and sildenafil by impacting patient relevant outcomes such as quality of life and dyspnea.

Given the limitations of the STEP-IPF study, including the low number of patients, further data is required in order to confirm the symptomatic benefits of sildenafil. In addition, this trial will allow the collection of safety and tolerability data of the combined treatment of nintedanib and sildenafil as well as of nintedanib alone in a population with advanced disease which has been typically excluded from the most recent clinical trials in IPF.

2.2 TRIAL OBJECTIVES

The primary objective is to assess efficacy and safety of concomitant treatment with nintedanib and sildenafil in IPF patients with advanced lung function impairment.

A further important objective of the trial is to enlarge the existing nintedanib mono-therapy database with safety and tolerability data in this population.

In addition, the effect of nintedanib and sildenafil on biomarkers related to IPF pathophysiology will be assessed to increase understanding of the mode of action of both compounds.

2.3 BENEFIT - RISK ASSESSMENT

All patients in this trial will be treated with nintedanib. As described in [section 1](#), patients with IPF may benefit from lesser decline in lung function and hence slower disease progression as a result of treatment with nintedanib. In addition, nintedanib significantly reduced the risk of a first acute exacerbation in 2 out of 3 clinical trials [[P11-11216](#), [P14-07514](#)].

Half of the patients in this trial will be treated with sildenafil in addition to nintedanib. In the STEP-IPF trial, sildenafil showed promising results in symptomatic or patient-related endpoints such as dyspnea and health-related quality of life [[R12-3686](#)].

Although currently unknown, concomitant treatment of both drugs may ultimately be found to add further benefits to patients.

The safety profile of nintedanib and sildenafil is described in [section 1.2](#).

The most common side effects of nintedanib are of gastrointestinal nature (diarrhoea, nausea, vomiting, abdominal pain), as well as liver enzyme elevations. Side effects are generally mild to moderate in nature. In case of side effects, symptomatic treatment, dose adjustments and/or interruptions of nintedanib should be considered to allow for resolution of the symptoms ([section 4.2.1](#)).

Risks of nintedanib treatment also include arterial hypertension, gastrointestinal perforations, thromboembolism, pancreatitis, thrombocytopenia and bleeding. Therefore, patients requiring full dose concomitant anticoagulation, fibrinolysis or high-dose antiplatelet therapy will be excluded from this trial.

The mode of action of nintedanib indicates a high potential for teratogenicity and/or embryotoxicity, including fetotoxicity/lethality. In women of childbearing potential receiving nintedanib, contraceptive measures must be employed 28 days before treatment initiation, during the treatment and for a period of 3 months after last drug intake.

The most common side effects of sildenafil are epistaxis, headache, dyspepsia, flushing, insomnia, erythema, dyspnea and rhinitis. Side effects are generally mild to moderate in nature. In case of side effects, symptomatic treatment and/or interruption of sildenafil should be considered to allow for resolution of the symptoms ([section 4.2.1](#)).

Potential risks of treatment with sildenafil include hypotension, worsening of pulmonary veno-occlusive disease, epistaxis, visual loss, hearing loss, priapism and vaso-occlusive crisis

in patients with pulmonary hypertension secondary to sickle cell disease. Patients at higher risk for these conditions are excluded from this trial.

Clinical data on the pharmacokinetics of nintedanib and sildenafil when given in combination is not available. Based on the known metabolic properties of both compounds, the likelihood of a pharmacokinetic drug-drug interaction is considered to be low. Nintedanib and its metabolites, BIBF 1202 and BIBF 1202 glucuronide, did not inhibit or induce CYP enzymes in vitro.

It is currently unknown if the co-administration of both drugs will result in additional side effects. To minimize this risk, safety monitoring in this trial will consist of regular visits to the investigational site, blood analyses and specific monitoring procedures to follow-up potential hepatic enzyme elevation. In addition, an independent data-monitoring committee (DMC) will review the safety data at specified intervals during the study conduct (refer to [section 3.1.1](#)).

Overall, the clinical safety profile of both nintedanib and sildenafil as established during the previous clinical trials is interpreted as favourable for the intended indication of IPF.

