Sildenafil is indicated for the treatment of Pulmonary Arterial Hypertension (PAH) in adults to improve exercise ability and delay clinical worsening. The efficacy of sildenafil was evaluated in four phase 3 short term studies (12 to 16 weeks), and included predominately patients with New York Heart Association (NYHA) Functional Class II–III symptoms. Etiologies were idiopathic (71%) or associated with connective tissue disease (25%). Based on the identification of different mechanistic pathways involved in the pathogenesis of pulmonary arterial hypertension, i.e. the nitric oxid, endothelin and prostaglandin pathways, increasing evidence suggests a role for sequential or upfront combination treatment in patients with PAH [[R15-5447](#)]. However, the effects of combination treatment of sildenafil with endothelin antagonists like macicentan or bosentan on morbidity and mortality are mixed [[R15-5445](#); [R15-5446](#)].

Sildenafil (20 mg tid) has also been studied in a 12 week double-blind placebo-controlled randomized trial followed by a 12 week period of open-label treatment which enrolled 180 IPF patients with advanced lung function impairment (STEP-IPF). Although this study met significant differences in some secondary endpoints such as quality of life, it failed to meet its primary outcome of change in 6-minute walk distance of $\geq 20\%$ at week 12 [[R12-3686](#)].

Safety data of sildenafil in adults were obtained from a 12-week, placebo-controlled clinical study and an open-label extension study in 277 patients with PAH, WHO Group I. The overall frequency of discontinuation in patients treated with sildenafil on 20 mg three times a day was 3% and was the same for the placebo group. Most common adverse reactions greater than or equal to 3% and more frequent than placebo were epistaxis, headache, dyspepsia,

flushing, insomnia, erythema, dyspnea, and rhinitis. Adverse reactions were generally transient and mild to moderate in nature.

Potential risks of treatment with sildenafil include hypotension, worsening of pulmonary veno-occlusive disease, epistaxis, visual loss, hearing loss, priapism and vaso-occlusive crisis in patients with pulmonary hypertension secondary to sickle cell disease.

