In the STEP-IPF study approximately 90% of patients in each group (sildenafil or placebo) had at least one adverse event with the most common being dyspnoea, cough and progression of IPF during the double-blind 12 weeks period. The proportion of serious adverse events was also similar between groups (15% in sildenafil vs. 16% in placebo) without significant between-group differences in the occurrence of specific serious adverse events [[R12-3686](#)].

Sildenafil is also indicated in adult men with erectile dysfunction with a recommended dose of 50 mg taken as needed approximately one hour before sexual activity. This dose will not be used in this study.

For a more detailed description of the drug profile refer to the current local Prescribing Information or Summary of Product Characteristics which is included in the Investigator Site File (ISF).

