3.3.3 Exclusion criteria

1. Previous enrolment in this trial;
2. ALT, AST > 1.5 fold upper limit of normal (ULN) at visit 1¹;
3. Total bilirubin > 1.5 fold ULN at visit 1¹;
4. Relevant airways obstruction (i.e. pre-bronchodilator FEV1/FVC < 0.7 at visit 1¹);
5. History of myocardial infarction within 6 months of visit 1 or unstable angina within 1 month of visit 1;
6. Bleeding Risk:
 - Known genetic predisposition to bleeding;
 - Patients who require fibrinolysis, full-dose therapeutic anticoagulation (e.g. vitamin K antagonists, direct thrombin inhibitors, heparin, hirudin, etc.) or high dose antiplatelet therapy²;
 - History of haemorrhagic central nervous system (CNS) event within 12 months prior to visit 1;
 - History of haemoptysis or haematuria, active gastro-intestinal bleeding or ulcers and/or major injury or surgery within 3 months prior to visit 1;
 - International normalised ratio (INR) > 2 at visit 1¹;
 - Prothrombin time (PT) and activated partial thromboplastin time (aPTT) $> 150\%$ of institutional ULN at visit 1¹;
7. Planned major³ surgery during the trial participation, including lung transplantation, major abdominal or major intestinal surgery;
8. History of thrombotic event (including stroke and transient ischemic attack) within 12 months of visit 1;

9. Creatinine clearance < 30 mL/min calculated by Cockcroft–Gault formula ([appendix 10.2](#)) at visit 1¹;
10. Presence of aortic stenosis (AS) per investigator judgement at visit 1;
11. Severe chronic heart failure: defined by left ventricular ejection fraction (EF) < 25% per investigator judgement at visit 1;
12. Presence of idiopathic hypertrophic subaortic stenosis (IHSS) per investigator judgement at visit 1;
13. Second-degree or third-degree atrioventricular (AV) block on electrocardiogram (ECG) per investigator judgement at visit 1;
14. Hypotension (systolic blood pressure [SBP] < 100 mm Hg or diastolic blood pressure [DBP] < 50 mm Hg) (symptomatic orthostatic hypotension) at visit 1;
15. Uncontrolled systemic hypertension (SBP > 180 mmHg or DBP > 100 mmHg) at visit 1¹;
16. Known penile deformities or conditions (e.g., sickle cell anemia, multiple myeloma, leukemia) that may predispose to priapism;
17. Retinitis pigmentosa;
18. History of vision loss;
19. History of nonarteritic ischemic optic neuropathy;
20. Veno-occlusive disease;
21. History of acute IPF exacerbation or respiratory infection within 8 weeks of visit 2.

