22. Treatment with nitrates, n-acetylcysteine, pirfenidone, azathioprine, cyclophosphamide, cyclosporine, prednisone >15 mg daily or >30 mg every 2 days OR equivalent dose of other oral corticosteroids as well as any investigational drug within 4 weeks of visit 2;
23. Treatment with prostaglandins (e.g., epoprostenol, treprostinil), endothelin-1 antagonists (e.g., bosentan, sitaxsentan, ambrisentan), phosphodiesterase inhibitors (e.g., sildenafil, tadalafil, vardenafil) or a stimulator of guanylatcylase (e.g., riociguat) within 4 weeks of visit 2;
24. Treatment with potent CYP3A4 inhibitors such as ketoconazole, itraconazole and ritonavir within 4 weeks of visit 2;
25. Supplementation with L-arginine and concurrent use of grapefruit juice or St John's wort within 4 weeks of visit 2;
26. Treatment with the reduced dose of nintedanib (100 mg bid) within 4 weeks of visit 2⁴;
27. Permanent discontinuation of nintedanib in the past due to adverse events considered drug-related;
28. Known hypersensitivity or intolerance to nintedanib, sildenafil, galactose, peanut or soya or any other components of the study medication;

29. A disease or condition which in the opinion of the investigator may interfere with testing procedures or put the patient at risk when participating in this trial;
30. Alcohol or drug abuse which in the opinion of the treating physician would interfere with treatment;
31. Women who are pregnant, nursing, or who plan to become pregnant while in the trial;
32. Women of childbearing potential⁵ not willing or able to use highly effective methods of birth control per ICH M3 (R2) that result in a low failure rate of less than 1% per year when used consistently and correctly⁶;
33. Patients not able to understand and follow study procedures including completion of self-administered questionnaires without help.
34. Patients with underlying chronic liver disease (Child Pugh A, B or C hepatic impairment)

¹ Laboratory parameters, blood pressure and lung function tests may be re-tested within the permitted timeframe, if found abnormal at Visit 1 and thought to be a measurement error or was the result of a temporary and reversible medical condition.

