3.3.4 Removal of patients from therapy or assessments

3.3.4.1 Removal of individual patients

An individual patient is to be withdrawn from trial participation if the patient withdraws consent for trial participation, without the need to justify the decision.

An individual patient is to be withdrawn from all trial drugs (nintedanib and sildenafil/matching placebo) if:

- The patient withdraws consent for study treatment, without the need to justify the decision;
- The patient needs to take concomitant drugs that interfere with the investigational products ([section 4.2.2](#));
- The patient can no longer be treated with trial medication for other medical reasons (such as surgery, adverse events, other diseases, or pregnancy);

If a patient becomes pregnant or pregnancy is suspected during the trial, the patient will be permanently discontinued from study treatment and will be followed up until birth or otherwise termination of pregnancy, please see [section 5.3.7](#).

- The patient experiences signs or symptoms of acute myocardial ischemia or stroke;
- The patient experiences signs of hepatic injury, defined as one of the following:
 - ALT and/or AST \geq 8 fold ULN
 - ALT and/or AST \geq 3 fold ULN and total bilirubin \geq 2 fold ULN
 - ALT and/or AST \geq 3 fold ULN and unexplained INR $>$ 1.5
 - ALT and/or AST \geq 3 fold ULN and unexplained eosinophilia ($>$ 5%)
 - ALT and/or AST \geq 3 fold ULN and appearance of fatigue, nausea, vomiting, right upper abdominal quadrant pain or tenderness, fever and/or rash.

For potential drug induced liver injury (DILI) follow up requirements please see [sections 4.2.1.3](#) and [5.3.6.1](#).

Treatment with nintedanib must be permanently discontinued in the following situations:

- In the opinion of the investigator, the patient experiences unacceptable toxicity due to nintedanib despite dose adjustments and supportive care;
- Gastrointestinal perforation;
- Major surgery including abdominal or intestinal surgery;
- Signs or symptoms of deep vein thrombosis or pulmonary embolism;
- Treatment interruption longer than 4 weeks (continuous).

In addition, permanent discontinuation of nintedanib should be considered in the following situations:

- Patient who requires full dose therapeutic anticoagulation or high dose antiplatelet therapy;
- Increased risk of bleeding (e.g., gross/ frank haemoptysis or haematuria, active gastrointestinal bleeding or ulcers).

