In such cases, continuation of nintedanib should be discussed with the patient and the decision based on an individual benefit-risk assessment documented in the source data.

Treatment with sildenafil/matching placebo must be permanently discontinued in the following situations:

- In the opinion of the investigator, the patient experiences unacceptable toxicity due to sildenafil despite supportive care;
- Hypotension (SBP < 100 mmHg or DBP < 50 mmHg) accompanied by symptoms;
- In the event of any sudden visual defect;
- Prolonged erections and priapism;
- Treatment interruption longer than 4 weeks (continuous).

If a patient discontinues all study drugs (nintedanib and sildenafil/matching placebo), he/she will undergo the procedures for early treatment discontinuation and will be invited to attend all planned study visits until week 24 as outlined in the [flow chart](#).

For all patients the reason for withdrawal (e.g. adverse events) must be recorded in the electronic case report form (eCRF). These data will be included in the trial database and reported.

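### Hearing loss is the only listed sildenafil risk with neither a related exclusion criterion nor a specific stopping rule, although section 2.3 says higher-risk patients are excluded

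*Protocol*

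**What the plan says.** Protocol section 2.3 states: "Potential risks of treatment with sildenafil include hypotension, worsening of pulmonary veno-occlusive disease, epistaxis, visual loss, hearing loss, priapism and vaso-occlusive crisis". The last item is qualified as applying to pulmonary hypertension secondary to sickle cell disease, and section 1.2.2 carries the same list. Section 2.3 continues directly: "Patients at higher risk for these conditions are excluded from this trial".

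The exclusion criteria are in section 3.3.3. On the visual side they include "History of vision loss" (criterion 18), next to retinitis pigmentosa (17) and nonarteritic ischemic optic neuropathy (19). Criterion 29 is a general clause: "A disease or condition which in the opinion of the investigator may interfere with testing procedures or put the patient at risk".

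Section 3.3.4.1 lists five situations in which sildenafil/matching placebo must be stopped for good: toxicity that the investigator finds unacceptable, symptomatic hypotension, a visual event ("In the event of any sudden visual defect"), prolonged erection or priapism, and a continuous interruption of more than 4 weeks. The same section provides for withdrawal from all trial drugs for other medical reasons, which include adverse events.

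For adverse events in general, section 4.2.1.1 says that a sildenafil-related event may call for an interruption of up to 4 weeks. After an interruption for an unrelated event, both drugs should be resumed at the previous dose.

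**The concern.** Visual loss and hearing loss are neighbours in the same risk sentence, but the protocol treats them differently. A sudden visual defect ends sildenafil/placebo by rule, whatever its cause. A sudden hearing loss does so only if the investigator, who does not know the treatment, judges that it amounts to unacceptable toxicity due to sildenafil or that the patient can no longer be treated, or if the drug stays interrupted for more than 4 weeks.

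Two things are at stake. First, a reader of the benefit-risk section, such as an ethics committee, is told that patients at higher risk of hearing loss are kept out, and no named criterion does that. Second, a patient with a sudden hearing loss could stay on sildenafil, or restart it within 4 weeks, in full compliance with the protocol. The monitoring of violations would not show it: item C6 in SAP Table 6.2:1 flags a failure to stop only when a criterion of section 3.3.4.1 was met.

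**Working it through.** No planned figure has to be reproduced. The check sets each risk listed in section 2.3 against the 34 exclusion criteria (section 3.3.3) and the five mandatory sildenafil/placebo stops (section 3.3.4.1).

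| Listed risk | Related exclusion criterion | Specific sildenafil/placebo stop |
|---|---|---|
| Hypotension | 14 | yes (with symptoms) |
| Worsening of veno-occlusive disease | 20 | none |
| Epistaxis | 6 (general bleeding risk; epistaxis not named) | none |
| Visual loss | 17, 18, 19 | yes (sudden visual defect) |
| Hearing loss | none | none |
| Priapism | 16 | yes |
| Vaso-occlusive crisis in sickle cell disease | 16 (sickle cell anemia is an example) | none |

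Counts:

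- Exclusion criteria that name hearing: 0 of 34. Criteria that concern vision or the eye: 3 of 34.
- Mandatory sildenafil/placebo stops that name hearing: 0 of 5. Stops that name vision: 1 of 5.
- Listed risks with a related exclusion: 6 of 7. With a specific stop: 3 of 7. With neither: 1 of 7, which is hearing loss.

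What then happens to a patient with a sudden hearing loss on treatment:

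1. *Judged unacceptable toxicity due to sildenafil, or a medical reason why treatment cannot go on.* The drug is stopped, and C6 would flag a failure to stop.
2. *Judged related but not unacceptable.* Section 4.2.1.1 makes interruption an option, so continuing, or restarting within 4 weeks, is allowed.
3. *Judged unrelated.* Interruption of up to 4 weeks is allowed, and the text then points towards resuming.
4. *Off drug continuously for more than 4 weeks.* The stop is mandatory, and C6 would flag a restart.

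Routes 2 and 3 are the gap. Under either, no criterion of section 3.3.4.1 has been met, so C6 has nothing to flag.

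**The case against.** Four arguments on the other side carry weight.

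*The protocol does not promise a named stop for every named risk.* This stands. Veno-occlusive disease, epistaxis and vaso-occlusive crisis have none either. A missing stop is therefore not an inconsistency in itself. What sets hearing loss apart is that it lacks both a stop and a related exclusion.

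*Nothing shows that a permanent stop is needed.* This also stands. The documents do not say that hearing loss on sildenafil is irreversible or that restarting is unsafe, and adjacency to visual loss in a list is not evidence of equal risk. Section 1.2.2 refers sites to the local sildenafil label in the Investigator Site File, and section 8.4.1 places the EU product information there as well. Either may advise on hearing. A reader might infer that sites have no guidance; the documents do not support that, because the label text is not visible.

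*General safeguards exist.* Criterion 29 can keep out a patient thought to be at risk, section 2.3 asks that interruption of sildenafil be considered for side effects, and an independent data monitoring committee reviews unblinded safety data. The causality guidance in section 5.3.6.1 would often point to relatedness for an unexplained event on a drug with that known risk. All true, but these provisions rest on judgement or act at trial level. They do not support a flat statement of exclusion, and the sponsor wrote explicit stops for hypotension, vision and priapism although the same safeguards cover those too.

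*No higher-risk group is shown to be admitted.* A reader might infer that vulnerable patients are being enrolled. The documents name no risk factor for hearing loss on sildenafil, so that cannot be claimed. The defect is in the assurance, which claims more than the criteria deliver.

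**Conclusion.** The point holds, as a minor one. The section 2.3 sentence is wrong as written for hearing loss, the only one of seven listed risks with neither a related exclusion criterion nor a specific mandatory stop. The absence of a hearing stop is not a demonstrated error; adding one is an inexpensive precaution in line with the visual-defect rule.

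The conclusion rests on the protocol and SAP text alone and on the label's content being unknown. The documents give no rate of hearing loss, so no number of affected patients can be derived from them. A reader might infer that safety data or the efficacy result are compromised. They are not: hearing events are collected and tabulated like any other adverse event, and the primary analysis does not depend on this rule.

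**What to change.** 1. In section 3.3.4.1, add a bullet to the mandatory sildenafil/matching-placebo stops, directly after the visual one: *any sudden hearing loss*.
2. In section 2.3, replace the general assurance with a sentence confined to what the criteria address, for example: *Excluded are patients with hypotension; veno-occlusive disease; a history of vision loss, retinitis pigmentosa or nonarteritic ischemic optic neuropathy; a condition predisposing to priapism, including sickle cell anemia; or a bleeding risk under criterion 6. A sudden hearing loss on treatment leads to permanent discontinuation of sildenafil/placebo.*

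SAP item C6 refers to section 3.3.4.1 as a whole, so it covers the new stop without a SAP change.

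The cost is one bullet and one sentence at the next amendment, plus a note to sites. No assessment is added and the sample size is unchanged. The downside is that some patients in either arm with a benign or unrelated hearing loss would stop sildenafil/placebo for good. With an assumed 24-week risk p of sudden hearing loss from any cause, the expected number is 250 × p over both arms: 0.25 at 0.1%, 1.25 at 0.5% and 2.5 at 1%. These rates are assumptions, and half of each number would be patients on placebo. The patients concerned can stay on nintedanib and keep their visits, and SAP section 7.4.1 keeps observations made after treatment discontinuation in the primary analysis.
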